### **7.3 Per Protocol Analysis Set for 12-month of Double-blind Period**

The per protocol analysis set will only be used to analyze the following endpoints: subject incidence of clinical fracture, new vertebral fracture, and nonvertebral fracture through Month 12 as sensitivity analyses. This subset includes subjects defined in [Section 7.1](#) (for new vertebral fractures) or [Section 7.2](#) (for clinical fracture and nonvertebral fracture) who receive active investigational product and did not violate any of the important inclusion/exclusion criteria for subject eligibility at enrollment per study important protocol deviation documents.

During the double-blind study period, for subjects who (a) received the investigational product not matching the subject's randomized treatment group, (b) had an investigational product related important protocol violation for romosozumab /placebo or ALN/placebo during the double-blind period, or (c) received proscribed therapy on study, all vertebral fracture data collected after the first occurrence of either of the above violations will be excluded from analysis; and nonvertebral and clinical fracture endpoints analyzed as time-to-event will be censored at the time of the first violation for subjects who have not had the fracture prior to the violation date. If subjects had an investigational product related important protocol deviation during the double-blind period, the violation date is determined as follows:

- if the subject is randomized to romosozumab, the time of violation for subjects missing > 3 doses of romosozumab is defined as the planned dosing date for the 4th (missed) dose or the subject's end of study date, whichever occurs first;
- if the subject is randomized to ALN, the first deviation date for "Less than 75% or more than 125% of planned ALN/placebo doses" IPD recorded in eClinical or the subject's end of study date, whichever occurs first.

The use of proscribed treatments will result in excluding or censoring the data from the per protocol analysis set. The list of proscribed treatments is provided in protocol Section 6.5.

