#### 6.1.1 Romosozumab/Placebo Dosage, Administration, and Schedule

During the 12-month double-blind ALN-controlled study period, subjects will receive 3 SC injections of romosozumab (ie, 3 injections of 70 mg romosozumab for a total dose of 210 mg) or matched placebo at each IP dosing visit (ie, Day 1 study visit and monthly study visits thereafter to Month 11). A separate PFS will be used for each injection; however, all 3 PFS to be used at a specific visit will be supplied in a single box, as assigned by the IVRS.

Injections will be administered by a healthcare professional into different sites on the subject's anterior abdominal wall, upper thigh, or upper arm. The injection should not be administered in the same arm from which blood is drawn. The romosozumab/placebo SC injection must be administered as the last procedure after all other study visit procedures have been completed. A physician must be available during administration of romosozumab/placebo. It is recommended that all subjects be closely observed for approximately 30 minutes after dosing with investigational product (IP).

The first dose of romosozumab/placebo should be administered on the day of randomization. If this is not possible, it must be administered within 72 hours of randomization.

Refer to specific instructions provided by the IVRS vendor for additional information on box assignment and to the IPIM for additional information regarding storage and preparation of IP.

Overdose with this product has not been reported. Neither the effects of overdose of romosozumab nor an antidote to overdose are known. The maximum amount of romosozumab that can be safely administered in a single dose has not been determined, and there is currently insufficient information to draw any conclusions about the safety of doses higher than those studied in clinical trials. The highest single dose of romosozumab tested in clinical trials is 10 mg/kg SC. Subjects who have received higher than protocol-defined doses should be carefully monitored for adverse events.

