**10.1.6.3 Per-protocol Analysis Set**

The per-protocol analysis set will only be used to analyze the following endpoints: subject incidence of clinical fracture, new vertebral fracture through Month 24, and nonvertebral fracture as sensitivity analyses for the primary analysis period and nonvertebral fracture for the overall study period. The per-protocol analysis set includes

subjects who are defined in [Section 10.1.6.1](#) (for new vertebral fractures in the primary analysis period) or [Section 10.1.6.2](#) (for clinical fracture and nonvertebral fracture in the primary or overall **study** analysis period) and receive the active investigational product with no major protocol violations in the corresponding analysis period. The major protocol violations will be defined in the Statistical Analysis Plan (SAP), and will be identified prior to study unblinding. Subjects in the per-protocol set will be analyzed according to their randomized treatment assignments.

**10.1.6.4 Primary Efficacy Analysis Set for BMD, Height, and PRO/ClinRO Endpoints for the Double-blind ALN-controlled Study Period and Primary Analysis Period**

This analysis set includes all randomized subjects who have a baseline and  $\geq 1$  post baseline evaluation at or before the time point under consideration. The efficacy analysis set may vary for different endpoints due to missing data. Subjects in the analysis set will be analyzed according to their randomized treatment assignments, regardless of treatment received.

**10.1.6.5 Safety Analysis Set for the Double-blind ALN-controlled Study Period, Primary Analysis Period, and Overall Study Period**

The safety analysis set includes all randomized subjects who receive  $\geq 1$  dose of investigational product in the 12-month of double-blind ALN-controlled study period. These subjects will be analyzed according to their actual treatment received, where subjects who received  $\geq 1$  dose of romosozumab will be analyzed in the romosozumab treatment group regardless of the randomized treatment.

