### **3. Study overview**

#### **3.1 Study Design**

This is a phase 3 multicenter, international, randomized, double-blind, ALN-controlled study of romosozumab in postmenopausal women with osteoporosis. The study is designed to evaluate if romosozumab treatment for 12 months followed by ALN treatment, compared with ALN treatment alone, is effective in reducing the incidence of clinical fracture (nonvertebral fracture and clinical vertebral fracture) and/or new vertebral fracture.

After signing the informed consent form (ICF), subjects will undergo a screening phase to complete eligibility assessments. Upon confirmation of eligibility, approximately 4,000 subjects will be randomized 1:1 (approximately 2,000 subjects per arm) to receive either 210 mg romosozumab subcutaneous (SC) every month (QM) or 70 mg ALN orally (PO) every week (QW) in a blinded fashion for the duration of the 12-month double-blind ALN-controlled study period. Randomization will be stratified by age (< 75 years, ≥ 75 years). Subjects will also receive matched placebo for either ALN or romosozumab. After the initial 12-month study period, subjects will receive ALN while

remaining blinded to their initial treatment assignment (romosozumab or ALN). The primary analysis period will end and the primary analysis will be performed when:

- clinical fracture events (nonvertebral fracture or clinical vertebral fracture) have been confirmed for at least 330 subjects  
AND
- all subjects have had the opportunity to complete their Month 24 study visit.

If more than 330 subjects have confirmed clinical fractures at the time each subject has completed her Month 24 visit, the primary analysis will be based on all available data, which may include more than 330 events.

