#### **7.4 Per Protocol Analysis Set for 24-Month Study Period, Primary Analysis Period, and Overall Study Period**

The per protocol analysis set will be used to analyze the clinical fracture, new vertebral fracture, and nonvertebral fracture through Month 24, clinical fracture and nonvertebral fracture at primary analysis, and nonvertebral fracture at final analysis (if the study continue to final analysis) as a sensitivity analysis. This subset includes subjects defined in [Section 7.1](#) (for vertebral fracture related endpoints) or [Section 7.2](#) (for nonvertebral related endpoints) who did not violate any of the important inclusion/exclusion criteria for subject eligibility at enrollment per study important protocol deviation documents.

For subjects who received (a) the investigational product not matching the subject's randomized treatment group during the double-blind period, (b) investigational product related important protocol violation for romosozumab/placebo or ALN/placebo during the

double-blind period, (c) investigational product related important protocol violation for open-label ALN during the open-label period of primary analysis period, or (d) proscribed therapy on study during the overall study period, all vertebral fracture data collected after the first occurrence of either of the above violations will be excluded from analysis; and nonvertebral and clinical fracture endpoints analyzed as time-to-event will be censored at the time of the first violation for subjects who have not had the fracture prior to the violation time. The use of proscribed therapies and investigational product related important protocol deviations during the double-blind period that will result in excluding or censoring the data from the per protocol analysis set is specified in [Section 7.3](#). In addition, if subjects had an investigational product related important protocol deviation during the open-label period, the violation date is determined as the first deviation date for “Less than 75% or more than 125% of planned ALN doses” IPD recorded in eClinical or the subject’s end of study date, whichever occurs first during the open-label period.

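### The per-protocol set counts violations of either product in either arm, but dates them only for each arm's active product, so censoring in the double-blind year follows different behaviour in the two arms

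*SAP*

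**What the plan says.** SAP 3.1 describes a double-dummy design: "Subjects will also receive matched placebo for either ALN or romosozumab". Protocol 6.1.1 has the injections given by a healthcare professional at dosing visits ("ie, Day 1 study visit and monthly study visits thereafter to Month 11"). Protocol 6.2.1 has the weekly tablets self-administered.

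SAP 7.3 lists the events after which vertebral data are excluded and time-to-event endpoints censored. Clause (b) applies to a subject who "had an investigational product related important protocol violation for romosozumab /placebo or ALN/placebo during the double-blind period". It names no arm. Two bullets then set the violation date:

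- "if the subject is randomized to romosozumab, the time of violation for subjects missing > 3 doses of romosozumab" is the planned date of the fourth missed dose, or the end of study if that comes first.
- "if the subject is randomized to ALN, the first deviation date for" the recorded deviation "Less than 75% or more than 125% of planned ALN/placebo doses", or the end of study if that comes first.

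SAP 7.4, which defines the set for Month 24 and for the primary analysis, repeats clause (b) and refers back to 7.3 for the first year: "The use of proscribed therapies and investigational product related important protocol deviations during the double-blind period that will result in excluding or censoring" is as specified there. For the open-label period, 7.4 adds a tablet rule that is the same in both arms. SAP 10.5.2.2 repeats both co-primary models on the 7.4 set. Its own description refers to subjects with an investigational-product deviation and names neither arm nor product.

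Protocol 10.1.6.3 contains no arm-specific adherence rule. It says: "The major protocol violations will be defined in the Statistical Analysis Plan (SAP), and will be identified prior to study unblinding". SAP section 11, which lists changes from the protocol, does not mention one either.

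**The concern.** In a double-dummy trial, an adherence rule applied alike to both products removes the same kind of woman from each arm when behaviour is the same in both. The dating bullets do not do this. They select on attendance for injections in one arm and on tablet-taking at home in the other. If the two products are missed at different rates, and women who miss doses fracture at a different rate, the per-protocol hazard ratio can move with no drug effect behind it.

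Two combinations of arm and product also meet clause (b) with no date attached. One programmer, following the bullets, would keep these women. Another, following clause (b) or 10.5.2.2, would have to invent a date.

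At stake is how the per-protocol result is read. It is one of two supportive analyses listed in 10.5.2.2 for new vertebral fracture and the only one listed there for clinical fracture.

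**Working it through.** **1. The plan's own figure.** SAP 3.2.2 gives 330 events for 90% power at HR 0.70, two-sided 0.05. Schoenfeld: 4 x (1.960 + 1.282)^2 / (ln 0.70)^2 = 331. Freedman gives 338. Power at 330 events is 0.900. The figure reproduces. It belongs to the full analysis set, so the per-protocol rule does not alter it.

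**2. Trigger against date.**

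| Arm | Injection | Tablets |
|---|---|---|
| Romosozumab | active: counted by (b), dated | placebo: counted by (b), no date |
| ALN | placebo: counted by (b), no date | active: counted by (b), dated |

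The limit for placebo injections is not stated; I take it to be the same, more than 3 missed. The tablet deviation is named for ALN/placebo, so it can be recorded in both arms.

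**3. Thresholds.** Day 1 to Month 11 is 12 injections. Missing 3 leaves 9/12 = 75.0% (allowed); missing 4 leaves 8/12 = 66.7% (violation). This is close to the 75% tablet floor. Only tablets have an upper limit, but six packs of 10 give 60 tablets against 52 weeks, 60/52 = 115%, so over the whole year the 125% limit is out of reach.

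**4. Share censored in the double-blind year.** The documents give no adherence rates. Assume 5% miss too many injections and 15% too many tablets, independently and alike in both arms. The bullets censor 5% of the romosozumab arm and 15% of the ALN arm. A rule on both products censors 1 - 0.95 x 0.85 = 19.3% of each.

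**5. Mechanism.** Let s and o be the injection and tablet non-adherence rates, and k the hazard ratio of non-adherers to adherers. If violators were removed outright and no later rule applied, a true HR of 1 would read (1 + o(k-1)) / (1 + s(k-1)). With s = 0.05, o = 0.15, k = 2: 1.15/1.05 = 1.095. With the rates reversed: 1.05/1.15 = 0.913. With k = 1 it is 1 whatever the rates.

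**6. Simulation with censoring times, true HR 1.**

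- Two million women per arm.
- Fracture rate 4.7% a year, from the SAP 3.2.2 ALN figures: 4% + 2.2%/3.
- Follow-up 24 to 58 months (24 minimum plus 34 for enrolment).
- Injection violations at months 4-12 and tablet violations at months 2-12.
- The common open-label tablet rule assumed to act at Month 18.

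| k | s | o | One rule, both arms | Bullets, with open-label rule | Bullets, without it |
|---|---|---|---|---|---|
| 1.5 | 5% | 15% | 1.001 | 1.008 | 1.033 |
| 1.5 | 10% | 15% | 0.999 | 0.986 | 1.016 |
| 1.5 | 5% | 25% | 1.003 | 1.019 | 1.072 |
| 1.5 | 15% | 5% | 1.000 | 0.958 | 0.969 |
| 2 | 5% | 15% | 1.001 | 1.012 | 1.072 |
| 2 | 10% | 15% | 0.996 | 0.980 | 1.034 |
| 2 | 5% | 25% | 0.994 | 1.035 | 1.130 |
| 2 | 15% | 5% | 0.998 | 0.923 | 0.941 |

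The column with the open-label rule corresponds to SAP 7.4 and runs from 0.92 to 1.04. A common rule gives 0.99-1.00 throughout. For scale, the standard error of log HR at 330 events is about 2/sqrt(330) = 0.110, and the largest shift is |ln 0.923| = 0.080, or 0.080/0.110 = 0.73 of it. The simulation covers the clinical-fracture hazard ratio; no figure was derived for the new vertebral fracture odds ratio.

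**The case against.** The best defence is that dating on the active product is deliberate. Protocol 10.1.6.3 and SAP 7.3 build the set around receiving active product, and missing placebo tablets does not reduce exposure to romosozumab. The lower thresholds also match closely, and the open-label rule is common to both arms. Any per-protocol set selects on behaviour after randomization, so a common rule would not turn it into a randomized comparison.

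Much of this stands: it limits the size, and an active-product definition is a legitimate choice. It does not remove the mismatch. Clause (b) counts placebo violations, and the SAP neither says they are to be ignored nor gives a reason. The deviation definitions are in separate documents, so how the undated women would be handled cannot be settled from the text.

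A reader might go further in three ways that the documents do not support:

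- **That adherence is plainly judged on one product per arm.** The trigger covers both products; only the dating is arm-specific.
- **That the ALN arm will lose more women and the hazard ratio will be pulled towards 1.** This needs tablets to be missed more often than injections, and poor adherers to be at higher risk. Neither is given. Larger shifts (up to 1.13 in the table) appear only if the open-label rule in 7.4 is left out.
- **That the rule breaches the requirement to identify violations before unblinding.** SAP 10.3 has the deviations defined and reviewed before database lock, and the tablet category is worded blind to arm. Applying a pre-specified date formula later identifies nothing new, and clause (a), receipt of the wrong product, also needs the treatment code.

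**Conclusion.** The point holds as a mismatch between trigger and date. Clause (b) reaches both products in both arms; the dates reach only each arm's active product. Two cells are left undated, and literal use of the bullets censors on different behaviour by arm during the double-blind year. Through 7.4 and 10.5.2.2 this enters the per-protocol repeats of both co-primary analyses. The primary analyses, alpha, power and decision rule are untouched.

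The size is modest and assumption-bound: about 0.92 to 1.04 for a true HR of 1, under the non-adherence rates and hazard ratios in the table. It does not follow that the per-protocol result would be uninterpretable. What follows is that a small difference from the primary result could come from the rule itself, in a direction that cannot be predicted.

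**What to change.** In SAP 7.3, and so in 7.4, drop the two conditions on randomized arm and use one rule for every woman, whether the product is active or placebo. The violation date is the earlier of:

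- the planned date of the fourth missed SC injection; and
- the first deviation date for "Less than 75% or more than 125% of planned ALN/placebo doses".

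Keep the end-of-study limit as it is, and bring the per-protocol wording in 10.5.2.2 into line. The adherence list and its dates can then be fixed without the treatment code, before unblinding. The active-product-only version can stay as an additional sensitivity analysis. If the sponsor wants that version as the main per-protocol rule, clause (b) should be narrowed to match, with a sentence giving the reason.

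The cost is SAP wording and a small program change. The per-protocol set becomes somewhat smaller, because some women are censored for missed placebo: in the example above, 19.3% of each arm in the double-blind year against 5% and 15%.

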#### **7.4 Per Protocol Analysis Set for 24-Month Study Period, Primary Analysis Period, and Overall Study Period**

The per protocol analysis set will be used to analyze the clinical fracture, new vertebral fracture, and nonvertebral fracture through Month 24, clinical fracture and nonvertebral fracture at primary analysis, and nonvertebral fracture at final analysis (if the study continue to final analysis) as a sensitivity analysis. This subset includes subjects defined in [Section 7.1](#) (for vertebral fracture related endpoints) or [Section 7.2](#) (for nonvertebral related endpoints) who did not violate any of the important inclusion/exclusion criteria for subject eligibility at enrollment per study important protocol deviation documents.

For subjects who received (a) the investigational product not matching the subject's randomized treatment group during the double-blind period, (b) investigational product related important protocol violation for romosozumab/placebo or ALN/placebo during the

double-blind period, (c) investigational product related important protocol violation for open-label ALN during the open-label period of primary analysis period, or (d) proscribed therapy on study during the overall study period, all vertebral fracture data collected after the first occurrence of either of the above violations will be excluded from analysis; and nonvertebral and clinical fracture endpoints analyzed as time-to-event will be censored at the time of the first violation for subjects who have not had the fracture prior to the violation time. The use of proscribed therapies and investigational product related important protocol deviations during the double-blind period that will result in excluding or censoring the data from the per protocol analysis set is specified in [Section 7.3](#). In addition, if subjects had an investigational product related important protocol deviation during the open-label period, the violation date is determined as the first deviation date for “Less than 75% or more than 125% of planned ALN doses” IPD recorded in eClinical or the subject’s end of study date, whichever occurs first during the open-label period.

## **7.5 Safety Analysis Set**

This safety analysis set includes all randomized subjects who receive  $\geq 1$  active dose of investigational product in the 12-month double-blind ALN-controlled study period. This analysis set will be used to analyze safety data for the double-blind study period, primary analysis period, and overall study period. AEs that begin on the end of double-blind period date will not be included in the 12-month double-blind study period. AEs that begin on the date of the end of primary analysis study period will be included in the primary analysis study period. These subjects will be analyzed according to their actual treatment received, where subjects who received  $\geq 1$  dose of romosozumab will be analyzed in the romosozumab treatment group regardless of the randomized treatment. The subject incidence rates for the primary analysis study period include all events that occurred in the double-blind study period and all events occurred on and before the end of primary analysis date for those subjects who received at least one dose of open-label ALN.

If the study continues to the final analysis, the subject incidence rates for the overall study period include all events that occurred in the double-blind study period and all events occurred in the open-label ALN period for those subjects who received at least one dose of open-label ALN.

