#### **End of Double-blind Period Date**

End of the double-blind period date is defined as the following:

1. First open-label ALN dose date if this date is prior to or on Study Day 366 + 30 days
  2. Month 12 visit date if subject did not receive the open-label ALN prior to or on Study Day 396 and this date is prior to or on Study Day 396 days
  3. End of study day or Study Day 396, whichever occurs first, for subjects who did not complete the Month 12 visit prior to study day 396 days
- The Month 12 visit date is defined as the latest assessment collected at Month 12.

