#### **Start of Open-label Period Date**

For subjects entering in the ALN open-label period, the end of double-blind period date is the beginning of the open-label period date. All scheduled

assessments occurring on this date are attributed to the double-blind period. The open-label ALN dose on the day is considered as occurring in the open-label follow-up period. Any adverse event or concomitant medication with a start date on this date is considered having started in the open-label follow-up period.

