### **Double-blind Period**

The time period from the enrollment date to the end of double-blind period date, inclusive

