### **Open-label ALN Period**

The time period from the end of double-blind period date to the end of study date, inclusive

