**Table 3. Imputation Rules on Incomplete Start Date of Adverse Event or Concomitant Medication**

	Missing	Impute	Exception
Start Date	Day	01	Default to Study Day 1 Date if the event started in the same year and month as Study Day 1
	Day / Month	01JAN	Default to Study Day 1 Date if the event started in the same year as Study Day 1
	Month	JAN	Default to Study Day 1 if the event started in the same year as Study Day 1
	Day / Month / Year	First Dose Date	Use randomization date for subjects who did not receive investigational product

If a death date (ie, End of Study date) is incomplete and missing only the day field, it will be imputed as the first day of the month if the latest date from other data is before the month of the death. However, if the latest assessment date is during the same month as the death, the partial death date will be imputed using the latest assessment date.

For dates of last period for menopause, the imputation rules for partial date are as follows: if the day is missing, default to day 15; if both month and day are missing, default to July 1. If the imputed date is on or after the randomization date, default to randomization date minus 1. Missing years will not be imputed.

If the date on the PRO administration page is partially or completely missing, the date of SC IP administration (or vital sign collection if SC IP is missing during the the double-blind period or during the open-label period) at the corresponding visit with the same CPEVENT will be used. Because it is expected that all PRO questionnaires be completed on the same day, EQ-5D-5L, BPI worst pain and LAD will use the same assessment date and the same imputation algorithm as that for OPAQ-SV.

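### Read as written, SAP 7.5 drops an adverse event that starts on the end of double-blind date from the 12-month table for every subject, in conflict with SAP 6.1.2 and 6.1.3

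*SAP*

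**What the plan says.** **The exclusion.** SAP 7.5 (Safety Analysis Set): "AEs that begin on the end of double-blind period date will not be included in the 12-month double-blind study period". No subgroup is named.

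**The hand-over rule.** SAP 6.1.2, in its entry on when open label starts, says: "For subjects entering in the ALN open-label period, the end of double-blind period date is the beginning of the open-label period date". For that date it adds: "Any adverse event or concomitant medication with a start date on this date is considered having started in the open-label follow-up period".

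**The periods.** SAP 6.1.3 defines the double-blind period as "The time period from the enrollment date to the end of double-blind period date, inclusive" and the open-label ALN period as "The time period from the end of double-blind period date to the end of study date, inclusive". Both contain the hand-over day.

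**The end date itself.** SAP 6.1.2 (End of Double-blind Period Date) uses the first open-label dose date, then the Month 12 visit date, each only if no later than Study Day 396. Failing both, it uses "End of study day or Study Day 396, whichever occurs first, for subjects who did not complete the Month 12 visit" by that day. SAP 9.2.6 treats the date of death as the End of Study date: "If a death date (ie, End of Study date) is incomplete".

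**Later periods.** The rate sentences in SAP 7.5 and 10.6.1 build the primary and overall periods from double-blind events plus later events in subjects with at least one open-label ALN dose. SAP 7.5 also says: "AEs that begin on the date of the end of primary analysis study period will be included in the primary analysis study period".

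**The concern.** The double-blind and open-label periods share a day, so a tie-break is needed. For a subject who goes on to open-label ALN it works: an event on that day leaves the 12-month period and is counted in the next one. For a subject who never takes open-label ALN, no later period picks the event up.

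The clearest case is a death before Month 12 from an event that began the same day. SAP 10.6.1 tabulates fatal events, and the primary safety hypothesis in SAP Section 5 concerns 12 months of romosozumab, so the 12-month table is where such an event is expected. Two programmers working from the same SAP, one from 7.5 and the other from 6.1.2 and 6.1.3, could produce different tables.

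**Working it through.** The plan gives no figure to reproduce. The check applies each rule to test cases, written as study days.

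**Case 1: death and AE onset both on Day 200; no Month 12 visit, no open-label ALN.**
- End of double-blind date = min(200, 396) = 200.
- 12-month table under 7.5 (onset must precede the end date): 200 < 200 is false, so the event is **excluded**.
- 12-month table under 6.1.3 (end date inclusive): 200 ≤ 200 is true, so it is **included**.
- 6.1.2: she does not enter the open-label period, so the event is not moved.
- Primary period: her end date is her End of Study date, Day 200, because 6.1.2 uses that date for early withdrawals. The rate sentence in 7.5 **omits** the event (not a double-blind event, no open-label ALN). The end-date sentence in 7.5, with the inclusive period in 6.1.3, **includes** it.
- Overall period: 6.1.2 (End of Final Analysis Period Date) and 6.1.3 **include** Day 200. The rate sentence **omits** the event.

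**Case 2: first open-label ALN dose and AE onset both on Day 366.**
- End of double-blind date = 366. SAP 7.5 excludes the event from the 12-month table, 6.1.2 moves it to open label, and the primary-period rate sentence counts it. Nothing is lost.

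**Case 3: Month 12 visit and AE onset on Day 366; stays on study, takes no open-label ALN.**
- End of double-blind date = 366. SAP 7.5 excludes the event from the 12-month table, and the primary-period rate sentence does not add it. SAP 6.1.3 would include it in the 12-month period. The outcome is the same on Day 396 for a subject still on study with no Month 12 visit.
- SAP 10.6 promises a listing of events after the double-blind period for subjects who stay on study without open-label ALN. It is unclear whether that listing covers the end day. It does not cover Case 1, because that subject did not remain on study.

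**Case 4: exit before Month 12 with an early-termination visit.**
- Protocol 7.3.13 combines the Month 12 and early-termination visits. If the visit is recorded as Month 12, the second rule in 6.1.2 sets the end date to that visit. Otherwise the third rule sets it to the End of Study date. In both cases an event starting on the end date meets the same exclusion, but the date need not be the day of exit.

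**Size of one omission.** With 2,000 subjects per arm, one omitted event changes an arm's incidence for that term by 1/2,000 = 0.05 percentage points. This holds only if she had no earlier occurrence of the same event in the period, since SAP 6.3 counts each subject once.

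**With the exclusion limited to recipients of open-label ALN,** Cases 1, 3 and 4 are counted in the 12-month table and Case 2 is unchanged.

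**The case against.** The best defence is that the sentence in 7.5 is shorthand for the hand-over rule in 6.1.2. That reading is possible and may be the intent. But 7.5 does not say so, and it is the section that governs the safety tables, so a programmer could reasonably apply it as it stands. What survives of the defence is that omission is not certain; it depends on which passage is programmed.

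The second defence is that the effect is close to nil. This largely stands. Only an event whose onset falls exactly on the end date is at issue.

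A reader might infer that deaths disappear from the report. The documents do not support that. SAP 10.2 tabulates reasons for study withdrawal, SAP 10.6.3 sends all deaths to adjudication, and a fatal event that began earlier stays in the table. SAP 10.6.3 does not say whether the same-day rule applies to adjudicated events, so nothing is concluded about them.

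A reader might also take the assumed first-year dropout, 10% of 4,000 = 400 subjects, as the size of the problem. It counts planned dropouts, not events that start on the end date, and the plan gives no rate for those.

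**Conclusion.** The SAP contains an unreconciled boundary rule. If 7.5 is programmed as written, AEs starting on the end of double-blind date are left out of the 12-month table for subjects who take no open-label ALN, including AEs that start on the day of a death before Month 12. For the primary and overall periods the SAP gives two answers, so it would be too strong to say that these events are lost from every table. It would also be too strong to infer bias between arms: the rule is identical in both, and nothing in the documents points to a direction. The conclusion rests on the literal wording of 7.5 and on 9.2.6 equating the date of death with the End of Study date. Severity: minor.

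Editorial note only: SAP 7.5 and 10.6 require an active dose for the safety set, while Protocol 10.1.6.5 and SAP 10.6.1 require a dose of investigational product, which under Protocol Section 6 includes placebo. A reader might infer a concealed change. That is not supported: the active-dose rule is stated openly, and 10.6 lists AEs of subjects without an active dose. It is only missing from SAP Section 11.

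**What to change.** In SAP 7.5, limit the same-day exclusion to subjects who received at least one dose of open-label ALN. For all other subjects, count AEs starting on the end of double-blind date in the double-blind period, and so in the primary and overall periods. Tie the limit to receipt of a dose rather than to entry: 6.1.2 does not define entry by a dose, and a subject who entered but took no tablet would still fall outside the rate sentences. Align the hand-over rule in 6.1.2 and the rate sentences in 7.5 and 10.6.1 with this.

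The cost is one sentence in 7.5, matching edits in two other sections, and minor reprogramming. No data collection changes.

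For the editorial note, use one dose wording in 7.5, 10.6 and 10.6.1, and list any departure from the protocol in Section 11.
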